7.8.2 Laboratory data

7.8.2.1 Standard laboratory analyses

The analyses of laboratory data will be descriptive in nature and will be based on BI standards ([13](#)). The variables to be recorded are listed in Section 5.2.3 of the CTP.

Analyses of laboratory variables will be displayed by patient group and overall, over the whole trial. Please refer to [Table 6.7: 1](#) for time windowing definition.

For data received from the central laboratory the respective reference ranges will be provided in the ISF.

For INR measurements, no reference range is transmitted by the central laboratory, because the central laboratory does not have information on concomitant medication taken by the patients, and the reference range for INR depends on whether a patient is taking anticoagulants. The reference ranges for INR will therefore be imputed with 0.8 for the lower limit of normal (LLN) and with 1.2 for the ULN, which correspond to the reference range defined by the central laboratory for patients not taking anticoagulants and which is more conservative than the range for patients taking anticoagulants (LLN=2, ULN=3).

The estimated Glomerular Filtration Rate (eGFR) is calculated based on serum creatinine according to Schwartz formula in children and adolescent (2-17 years old) and according to CKD/EPI formula in adults (see CTP Sections 5.2.3 and 10.3). As the parameter (eGFR) evaluated is the same and just the formula are chosen appropriately as recommended per age, for the analyses these two methods of calculation are considered to result in the same parameter.

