3.3.3 Exclusion criteria

For new patients:

1. AST and/or ALT >1.5 x ULN at Visit 1.
2. Bilirubin >1.5 x ULN at Visit 1.
3. Estimated Glomerular Filtration Rate (eGFR) <30 mL/min/1.73m² at Visit 1 (please refer to [Appendix 10.3](#)).

[Note: Laboratory parameters from Visit 1 have to satisfy the laboratory threshold values as shown above. Visit 2 laboratory results will be available only after the visit In case, at Visit 2, the results do no longer satisfy the entry criteria, the Investigator has to

decide whether it is justified that the patient remains on study drug. The justification for decision needs to be documented. Laboratory parameters that are found to be abnormal at Visit 1 are allowed to be re-tested (once) if it is thought to be a measurement error (i.e. there was no abnormal result of this test in the recent history of the patient and there is no related clinical sign) or the result of a temporary and reversible medical condition, once that condition is resolved.]

4. Patients with underlying chronic liver disease (Child Pugh A, B or C hepatic impairment) at Visit 1.
5. Other investigational therapy received within 1 month or 5 half-lives (whichever is shorter but ≥ 1 week) prior to Visit 2 except investigational therapy received in InPedILD[®] trial.
6. Significant pulmonary arterial hypertension (PAH) defined by any of the following:
 - a. Previous clinical or echocardiographic evidence of significant right heart failure
 - b. History of right heart catheterization showing a cardiac index ≤ 2 l/min/m²
 - c. PAH requiring parenteral therapy with epoprostenol/treprostinil
7. In the opinion of the Investigator, other clinically significant pulmonary abnormalities.
8. Cardiovascular diseases, any of the following:
 - a. Severe hypertension, uncontrolled under treatment, within 6 months of Visit 1.
Uncontrolled hypertension is defined as
 - i. In children 6 to ≤ 12 years old: ≥ 95 th percentile + 12 mm Hg or $\geq 140/90$ mm Hg (whichever is lower) (systolic or diastolic blood pressure equal to or greater than the calculated target value) (please refer to [Appendix 10.5](#)). Not applicable in France.
 - ii. In adolescents 13 to 17 years old: systolic blood pressure ≥ 140 mm Hg or diastolic blood pressure ≥ 90 mm Hg (please refer to [Appendix 10.5](#)). In France, applicable for adolescents 12 to 17 years old.
 - b. Myocardial infarction within 6 months of Visit 1
 - c. Unstable cardiac angina within 6 months of Visit 1

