10.3 ESTIMATED GLOMERULAR FILTRATION RATE

- Calculation of eGFR according to Schwartz Formula in adolescents 13-17 years old [[R10-0828](#)]

Conventional:

- in adolescent males $k=0.70$:

$$\text{eGFR (mL/min./1.73m}^2\text{)} = \text{height (cm)} \times 0.70 / \text{serum creatinine (mg/dL)}$$

- in adolescent females $k=0.55$:

$$\text{eGFR (mL/min./1.73m}^2\text{)} = \text{height (cm)} \times 0.55 / \text{serum creatinine (mg/dL)}$$

SI:

- in adolescent males $k=0.70$:

$$\text{eGFR (mL/min./1.73m}^2\text{)} = \text{height (cm)} \times 0.70 / (\text{serum creatinine } (\mu\text{mol/L)} \times 0.01131)$$

- in adolescent females $k=0.55$:

$$\text{eGFR (mL/min./1.73m}^2\text{)} = \text{height (cm)} \times 0.55 / (\text{serum creatinine } (\mu\text{mol/L)} \times 0.01131)$$

Calculation of eGFR according to Schwartz Formula in children 2-12 years of age [[R11-4789](#)]:

Conventional:

- in children 2-12 years of age $k=0.41$:

$$\text{eGFR (mL/min./1.73m}^2\text{)} = \text{height (cm)} \times 0.41 / \text{serum creatinine (mg/dL)}$$

SI:

- in children 2-12 years of age $k=0.41$:

$$\text{eGFR (mL/min./1.73m}^2\text{)} = \text{height (cm)} \times 0.41 / (\text{serum creatinine } (\mu\text{mol/L)} \times 0.01131)$$

Calculation of eGFR according to CKD/EPI formula in adults [[R12-1392](#)]:

Conventional:

$$\text{eGFR (mL/min./1.73m}^2\text{)} = 141 \times \min(\text{SCr}/\kappa, 1)^\alpha \times \max(\text{SCr}/\kappa, 1)^{-1.209} \times 0.993^{\text{Age}} \times 1.018 \text{ [if female]} \times 1.159 \text{ [if Black]}$$

SCr = standardized serum creatinine (mg/dL)

κ = 0.7 (females) or 0.9 (males)

α = -0.329 (females) or -0.411 (males)

min = indicates the minimum of SCr/ κ or 1

max = indicates the maximum of SCr/ κ or 1

age = years

SI:

$$\text{eGFR (mL/min./1.73m}^2\text{)} = 141 \times \min(\text{SCr}/\kappa, 1)^\alpha \times \max(\text{SCr}/\kappa, 1)^{-1.209} \times 0.993^{\text{Age}} \times 1.018 \text{ [if female]} \times 1.159 \text{ [if Black]}$$

SCr = standardized serum creatinine ($\mu\text{mol/L}$)

κ = 61.9 (females) or 79.6 (males)
 α = -0.329 (females) or -0.411 (males)
min = indicates the minimum of SCr/κ or 1
max = indicates the maximum of SCr/κ or 1
age = years

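### The SAP pools eGFR as one parameter, but Appendix 10.3 uses two Schwartz versions that differ by 34% (girls) or 71% (boys) across age 13, so baseline eGFR summaries partly reflect age and formula mix

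*SAP*

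**What the plan says.** - **SAP 7.8.2.1** calculates eGFR from serum creatinine "according to Schwartz formula in children and adolescent (2-17 years old) and according to CKD/EPI formula in adults", referring to Protocol 5.2.3 and 10.3. It reasons that each formula suits its age group and concludes that "these two methods of calculation are considered to result in the same parameter". The same section displays laboratory variables by patient group and overall.
- **Protocol Appendix 10.3** has three blocks. The first is headed "Calculation of eGFR according to Schwartz Formula in adolescents 13-17 years old" and uses a constant of 0.70 in males and 0.55 in females, from a source that the reference list dates 1987. The second is headed "Calculation of eGFR according to Schwartz Formula in children 2-12 years of age" and uses 0.41 for both sexes, from a different source dated 2009. The third is CKD/EPI for adults.
- **Protocol 5.2.3** cites both Schwartz sources, but its text assigns the formula to adolescents only and does not mention younger children. Table 5.2.3:1 restricts eGFR to Visits 1 and 2. Creatinine carries no such restriction.
- **Protocol 3.3.3, exclusion criterion 3**, excludes new patients with "Estimated Glomerular Filtration Rate (eGFR) <30 mL/min" per 1.73 m² at Visit 1 and points to Appendix 10.3. It is not among the exclusion criteria listed for roll-over patients.

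**The concern.** The SAP's description implies one scale up to age 17 and a single change of formula at 18. Appendix 10.3 has a further change at 13, inside what the SAP calls one method, and the SAP does not mention it. It plans no split by formula and no display using a single formula.

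The formula mix can also differ between the two analysis groups because of the design. New patients must be 6 to 17 years old and all fall in Group 1. Patients from the parent trial who roll over are not held to that age criterion, and Protocol 3.3.1 allows those who reached adult age there. Group 2 consists entirely of roll-over patients. Group 1 can also contain some adults, through former placebo patients and completers who came over late, so the contrast is one of proportion. Protocol 7.2.6 plans a descriptive comparison of laboratory data between groups, and a reader of that table could take a formula difference for a difference in kidney function.

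The second consequence is that criterion 3 sets one eGFR cut-off, which corresponds to different creatinine levels on either side of age 13.

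**Working it through.** The documents give no figure for the size of the step, so there is none to reproduce. The inputs are the Appendix 10.3 constants and its formula, eGFR = k × height (cm) / creatinine (mg/dL).

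**Step at age 13, height and creatinine held fixed.** Height and creatinine cancel, leaving the ratio of constants:
- girls: 0.55 / 0.41 = 1.341, or +34.1%
- boys: 0.70 / 0.41 = 1.707, or +70.7%

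**Illustration at ordinary values** (assumed 155 cm and 0.6 mg/dL):
- age 12: 0.41 × 155 / 0.6 = 105.9
- girl of 13: 0.55 × 155 / 0.6 = 142.1
- boy of 13: 0.70 × 155 / 0.6 = 180.8

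**Effect on a group mean.** Suppose two groups have identical heights and creatinines, and one has 10 percentage points more patients in the 13-17 band instead of the 2-12 band. Its mean eGFR is then higher by 0.10 × 34.1% = 3.4% of the 2-12 value if those patients are girls, or 0.10 × 70.7% = 7.1% if they are boys. This isolates the formula. Real heights and creatinines also change with age, so it does not predict the observed difference.

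**Step at 18** (Appendix 10.3 CKD/EPI; assumed heights 172 cm for males and 162 cm for females, creatinine 0.5 to 2.5 mg/dL, no race factor). The change on leaving Schwartz is about -7% to -34% in males and -1% to -24% in females. For a male at 0.6 mg/dL, Schwartz gives 0.70 × 172 / 0.6 = 200.7. CKD/EPI gives 141 × (0.6/0.9)^-0.411 × 0.993^18 = 146.8, which is 27% lower. At fixed height and creatinine, the pooled parameter therefore steps up at 13 and down at 18.

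**Creatinine equivalent to eGFR 30**, that is k × height / 30:

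| Assumed height | Age 12 | Girl of 13 | Boy of 13 |
|---|---|---|---|
| 145 cm | 1.98 | 2.66 | 3.38 |
| 155 cm | 2.12 | 2.84 | 3.62 |
| 160 cm | 2.19 | 2.93 | 3.73 |

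At 155 cm and 2.5 mg/dL, eGFR is 0.41 × 155 / 2.5 = 25.4 at age 12 (excluded). It is 34.1 for a girl of 13 and 43.4 for a boy of 13 (neither excluded by criterion 3).

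**Would the planned tables reveal the mix?** Only in part. The age categories in SAP 5.4.1.1 are 6 to under 12, 12 to under 18, and 18 or over. Twelve-year-olds, who take the constant 0.41, share a category with ages 13-17, who take 0.55 or 0.70.

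**The case against.** The strongest reply is that age- and sex-specific constants are meant to map the same creatinine to different filtration rates, so a ratio at fixed creatinine is no proof of artefact. By the same test, boys and girls of 13-17 differ by 0.70/0.55 = 1.27, or 27%, and nobody would object to that. Deciding how much of the step at 13 is intended would need the two source papers and the laboratory's creatinine method, and the documents supply neither. This stands: nothing here shows that either version is wrong.

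It is also true that the SAP's two methods are Schwartz and CKD/EPI, which change over at 18. Deleting that sentence alone would leave the step at 13 unaddressed. Creatinine is already among the laboratory variables analysed by group, age is tabulated by group, and no testing is planned. These points reduce the consequence.

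They do not remove the problem. The SAP bases its equivalence claim on a description that leaves out one of the versions in use, so it has not considered whether those values belong in one summary. SAP 7.8.3 declines to summarise sitting height and leg length across patients because the measurement method was inconsistent. For eGFR the inconsistency can be calculated from the protocol, yet the values are pooled.

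**Conclusion.** The point holds as a gap in the specification of a baseline safety display. At fixed height and creatinine the two Schwartz versions differ by 34% in girls and 71% in boys across age 13. That result rests only on the constants in Appendix 10.3. The creatinine equivalents and the step at 18 rest on the assumed heights and creatinines shown. The change is worth making because it is cheap. It has no bearing on the primary endpoint, the incidence of treatment-emergent adverse events.

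A reader might infer more, and the documents do not support it:
- **That patients' eGFR will jump during follow-up.** No eGFR is scheduled after Visit 2. For roll-over patients Visits 1 and 2 should fall on the same day. For new patients screening may last at most 12 weeks, so a 13th birthday between the two visits would be rare.
- **That adolescent values are inflated, or childhood values too low.** The documents cannot show which version is right.
- **That unsuitable patients were admitted, or suitable ones excluded.** Criterion 3 applies only to patients held to the new-patient exclusion criteria. Few of them are likely to be near 30, and the documents give no count.

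**What to change.** **SAP 7.8.2.1.** Replace the statement that the methods give the same parameter. Replacement text could read:

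> eGFR is derived by the three age-specific calculations in Protocol Appendix 10.3 (ages 2-12, ages 13-17, adults). Values from different calculations are not assumed to be interchangeable. eGFR will be summarised by patient group and overall within each of these bands, next to serum creatinine.

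The cost is some SAP wording and one extra split of one table. Cells will be small: 50 to 60 patients over two groups and three bands average about 8 to 10 per cell (50/6 = 8.3, 60/6 = 10), and some may be nearly empty. That is acceptable for a descriptive display.

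**Protocol.** Appendix 10.3, the text of 5.2.3 and exclusion criterion 3 should be reconciled. Section 5.2.3 should cover every age group that Appendix 10.3 covers. The sponsor should state whether it intends the single cut-off to correspond to different creatinine levels on either side of age 13. No formula or threshold is proposed here. If enrolment of new patients has ended, which the documents do not say, this part has little practical effect and the SAP change is the one that matters.

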7.8.2.2 Liver enzyme and bilirubin elevations

A thorough description of liver enzymes and bilirubin elevations, as defined in [Section 5.4.4](#), will be given over the whole trial by patient group and overall, including:

[figure not shown]
- Summary table of liver enzyme elevation
- Summary of signs of hepatic injury (see [Section 5.4.4](#))
- Summary table of individual maximum liver enzyme and bilirubin elevations
- Time to first onset and number of patients with liver enzyme elevation. The time to onset of first liver enzyme and bilirubin elevation [days] will be summarised according to both, quartiles from Kaplan-Meier curve
- Kaplan-Meier plot of time to first liver enzyme elevation. No statistical test will be performed. Separate plots will be presented by patient group and overall.
- Single time course profiles of liver enzymes and other laboratory parameters (ALT, AST, alkaline phosphatase, total bilirubin, eosinophils/ leukocytes, GGT) for all patients (maximum individual elevations given in [Section 5.4.4](#)).
- Graphical displays of potential Hy's law cases

[figure not shown]

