- 19. Patients <13.5 kg of weight at Visit 1 (same threshold to be used for male and female patients).

For roll-over patients from the InPedILD[®] study:

Only criteria 11, 12, 13, 15, 16, 17 and 19, listed for new patients are applicable with the following additional exclusion criterion:

- 20. Patient not compliant in parent trial (InPedILD[®]), with trial medication or trial visits, according to investigator's judgement.

Roll-over patients may qualify for participation even though other exclusion criteria may have been met during the participation in InPedILD[®], if the investigator's benefit-risk assessment for the individual patient remains favourable. This should be discussed with sponsor before the roll-over of patient.

For patients who prematurely discontinued treatment permanently in 1199-0337 but are potentially eligible and for completed patients from parent trial not able to roll over into the extension trial within 12 weeks following their End of Treatment Visit in the parent trial:

All exclusion criteria for new patients are applicable. In addition, the following additional exclusion criterion is applicable for patients who prematurely discontinued treatment permanently in 1199-0337:

- 21. Patients who experienced drug-related adverse events during parent trial leading to permanent study treatment discontinuation.

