5.4.4 Liver enzyme and bilirubin elevations

Liver enzyme and bilirubin elevations will be reported using the following definitions:

- (ALT and/or AST ≥ 3 fold ULN) and bilirubin ≥ 2 fold ULN ^[1]
- ALT ≥ 5 fold ULN and/or AST ≥ 5 fold ULN
- ALT ≥ 3 fold ULN and/or AST ≥ 3 fold ULN

^[1] within a time window of 30 days i.e. the elevation of bilirubin should appear within 30 days after the elevation of AST and/or ALT

The proportion of patients presenting signs of hepatic injury will be summarised, based on the following definition for signs of hepatic injury:

- ALT and/or AST ≥ 8 fold ULN
- ALT and/or AST ≥ 3 fold ULN and total bilirubin ≥ 2 fold ULN ^[2]
- ALT and/or AST ≥ 3 fold ULN and unexplained INR > 1.5 ^[2]
- ALT and/or AST ≥ 3 fold ULN and unexplained eosinophilia ($> 5\%$) ^[2]

- ALT and/or AST ≥ 3 fold ULN and appearance of fatigue, nausea, vomiting, right upper abdominal quadrant pain or tenderness, fever and/or rash within +/- 7 days of the abnormal ALT and/or AST laboratory test result (please refer to [Table 10.5: 1](#) for the list of relevant MedDRA preferred terms to support the derivation of a potential hepatic injury)

^[2] in the same blood draw sample

In addition, maximum individual elevations based on worst value on treatment will be defined as:

- ≥ 3 fold ULN; ≥ 5 fold ULN; ≥ 8 fold ULN for AST and ALT and AST and/or ALT
- ≥ 1.5 fold ULN; ≥ 2 fold ULN for Bilirubin
- ≥ 1.5 fold ULN; ≥ 2 fold ULN for alkaline phosphatase (ALK)
- ≥ 3 fold ULN for Gamma-Glutamyl-Transferase (GGT)

Note: ULN refers to the Upper Limit of Normal from the central or local laboratory analysing samples.

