5.4.4.1 Time-to-event analyses for liver enzyme elevations

- Time to liver enzyme and bilirubin elevation (ALT and/or AST $\geq 3xULN$ and bilirubin $\geq 2xULN$)
- Time to liver enzyme elevation (ALT and/or AST $\geq 5xULN$)
- Time to liver enzyme elevation (ALT and/or AST $\geq 3xULN$)

Time to first occurrence of the above described liver enzyme elevations [days] is derived based on first trial drug intake as

$$\text{Date of event/censoring} - \text{Date of first trial drug intake [days]} + 1 \text{ day.}$$

Patients with no such event documented will be censored according to the mechanism for censoring as described in [Table 5.4.4.1: 1](#).

Table 5.4.4.1: 1 Censoring rules for time to first occurrence of liver enzyme elevations

Rule #	Situation	Outcome (Event/Censored)	Date of event/censoring
1	Patient had a documented event before permanent trial drug discontinuation (or within the 28 days after permanent trial drug discontinuation)	Event	Earliest date of event
2	Patient had no documented event before permanent trial drug discontinuation (or within the 28 days after permanent trial drug discontinuation).	Censored	Earliest date of 
 • last trial drug intake + 28 days, • derived date of last contact when patient was known to be alive, • date of death.
3	Patient neither had a documented event nor terminated trial drug permanently (only applicable for potential interim analyses)	Censored	Date of interim data snapshot

These times will also be summarised in categories [weeks] as defined for duration of exposure [weeks] in [Section 5.4.3](#).

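### The liver elevation outputs have no baseline condition, so a roll-over patient already above a threshold can be shown as an on-treatment elevation and, for ALT/AST-based events, as an early first onset

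*SAP*

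**What the plan says.** **Definitions.** SAP 5.4.4 sets every liver category as a fixed multiple of ULN, for example "ALT ≥ 3 fold ULN and/or AST ≥ 3 fold ULN". For the individual maxima it states that "maximum individual elevations based on worst value on treatment will be defined as" multiples of ULN: 3, 5 and 8 for ALT/AST, 1.5 and 2 for bilirubin and ALK, and 3 for GGT.

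**Curves.** SAP 5.4.4.1 covers three events: ALT/AST at least 3 x ULN, ALT/AST at least 5 x ULN, and the composite of ALT/AST at least 3 x ULN with bilirubin at least 2 x ULN. "Time to first occurrence of the above described liver enzyme elevations [days] is derived based on first trial drug intake". The three event and censoring rules refer to drug discontinuation, last contact, death and the interim snapshot. None refers to baseline.

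**On-treatment.** SAP 7.8 assigns a measurement to the on-treatment period by date alone, from first intake to 28 days after last intake. SAP 7.8.2.2 lists a "Summary table of individual maximum liver enzyme and bilirubin elevations" and describes the time-to-event output as time to first onset.

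**Entry limits.** New patients are excluded for "AST and/or ALT >1.5 x ULN at Visit 1", with the same limit for bilirubin (protocol 3.3.3, criteria 1 and 2). For roll-over patients, "Only criteria 11, 12, 13, 15, 16, 17 and 19, listed for new patients are applicable", plus criterion 20 on compliance. Criteria 1, 2 and 4, which concern the liver, are not on that list. No criterion limits ALK or GGT in any cohort.

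**The concern.** A worst-value rule without a baseline condition cannot separate an elevation that arises in the extension from one that the patient brings into it. For a new patient the ALT/AST and bilirubin entry limits largely close that gap. For a roll-over patient they do not.

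Two readings are at stake. A percentage in a worst-value table may include persisting elevations. An early step in a curve of first onset may be an elevation that began in the parent trial. The early part of such a curve attracts attention, because protocol 1.2 says that most hepatic events in adults occur in the first three months of treatment. Long-term safety is the main objective of the trial and hepatic injury is an adverse event of special interest, so these outputs will be read closely.

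**Working it through.** The plan states no liver event rate or count, so there is no figure to reproduce. The check sets the rules side by side and then sizes one patient.

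**1. Can a roll-over patient start above a threshold?** Yes. Criteria 1 and 2 do not apply (protocol 3.3.3). Protocol Table 4.2.1.2:1 has a separate Visit 2 row for new patients, but places roll-over patients at every visit in the row for elevations under treatment. An elevation at Visit 2 in a roll-over patient is thus handled by the management rules and is not an entry bar.

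**2. When is that patient counted?** The pre-dose sample is baseline (SAP 6.7) and not on-treatment. A carried-over elevation counts only if at least one sample after first intake is still at or above the threshold. Values taken during an interruption also count, since SAP 7.8 runs from first to last intake plus 28 days.

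**3. What event time results?** Time = date of event − date of first intake + 1 day. Take a roll-over patient with ALT at least 3 x ULN before the first extension dose and at the next sample:

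| Next sample | Event day |
|---|---|
| Retest 48 to 72 hours after Day 1 (assumed start of that interval) | 2 + 1 = 3 to 3 + 1 = 4 |
| Visit 3 (less than 26 weeks in the parent trial) | 15 |
| Visit 4, if Visit 3 does not apply and no earlier sample is taken | 85 |

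**4. Which outputs are touched?**

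| Parameter | Worst-value table | Curve | Entry limit differs by cohort |
|---|---|---|---|
| ALT/AST | yes | yes | yes |
| Bilirubin alone | yes | no | yes |
| ALT/AST with bilirubin | summary of elevations | yes | yes |
| ALK, GGT | yes | no | no (no limit for anyone) |

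**5. Which groups?** Group 2 (continued nintedanib) consists of roll-over patients. Group 1 (initiated nintedanib) also contains roll-overs from the placebo arm of Part A (SAP 7), who are equally exempt from criteria 1 and 2.

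**6. How large?** The number k of patients elevated at entry and again after first intake is not given. With 50 to 60 patients in total (protocol synopsis) and no new elevation at all, the reported overall percentage is 100 × k / n:

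| k (assumed) | n = 50 | n = 60 |
|---|---|---|
| 1 | 2.0% | 1.7% |
| 2 | 4.0% | 3.3% |
| 3 | 6.0% | 5.0% |

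The sizes of Groups 1 and 2 are not stated. If Group 2 had 30 patients, one case would be 1/30 = 3.3%. That is an assumption: 30 is the expected minimum of all roll-overs, including any from the placebo arm.

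**7. Does the plan handle baseline elsewhere?** Yes, twice. The footnote to the exposure analyses in SAP 5.4.3 limits time to first dose reduction to patients who started on full dose for their weight. Protocol 7.2.6 treats an adverse event that began before first intake as treatment-emergent only if it deteriorates. An unchanged liver adverse event from the parent trial would therefore not be treatment-emergent in the adverse event tables, while the same patient's laboratory values could count as a first onset in the liver output.

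**The case against.** The case for leaving the plan alone has several parts.

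- **Fixed ULN multiples are deliberate.** The protocol defines hepatic injury the same way (5.2.7.1.4), and the worst on-treatment value is the cautious choice for safety. This stands, and is why the existing tables should stay.
- **Such patients should be few and known.** Entry of a roll-over patient who met other exclusion criteria in the parent trial needs a favourable benefit-risk assessment and discussion with the sponsor. Criterion 13 still applies, and elevations of at least 3 x ULN trigger action under Table 4.2.1.2:1. This supports calling the ALT/AST case rare. It does not change how a case is counted.
- **Context exists elsewhere.** SAP 7.8.2.2 plans individual time courses for all patients, so a carried-over elevation can be found case by case. The standard laboratory tables follow a company standard that is not available here and might include shifts from baseline. Neither is stated to alter the liver tables or curves.
- **Dropping baseline-elevated patients could hide toxicity.** An elevation at entry in Group 2 may have arisen on nintedanib in the parent trial, and a patient who normalises and rises again would be lost. This stands. Any restricted curve should be an addition.

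A reader might infer that Group 2 will look worse than Group 1 on every liver parameter. The documents do not support that. ALK and GGT have no entry limit for anyone, bilirubin alone has no curve, and exempt roll-overs sit in both groups. Nor do they support any particular inflated percentage, because no count of elevated entrants is given.

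**Conclusion.** The gap is real and limited. SAP 5.4.4, 5.4.4.1 and 7.8.2.2 use no baseline value, although SAP 6.7 defines one. A roll-over patient above a threshold before and after the first extension dose is shown as an on-treatment elevation in the tables and, for the three ALT/AST-based events only, as an early first onset.

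Each such patient adds about 1.7 to 2.0 percentage points to the overall column. That is illustrative: it assumes 60 or 50 treated patients and a post-dose value still over the threshold. The unequal entry limit concerns ALT/AST and bilirubin, and affects roll-over patients in Group 2 and the placebo Part A roll-overs in Group 1. For ALK and GGT the issue is only whether the elevation persisted or arose in the trial.

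The effect is confined to descriptive safety output. Parts of the SAP are blacked out, but the sections relied on here are readable and contain no baseline rule. This is an inexpensive improvement worth making, and it does not undermine the primary analysis.

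**What to change.** In SAP 5.4.4, 5.4.4.1 and 7.8.2.2:

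1. Keep the worst-value tables. Add, for each threshold, a display by SAP 6.7 baseline status: below, at or above, or missing. Describe only a change from below to at or above as newly emerging. The missing category is needed because Table 6.7: 1 limits the baseline window to Day -35 to Day 1.
2. Keep the all-patient time-to-first curves. Add a version of each restricted to patients below that threshold at baseline. For the composite, restrict to patients who do not meet the full composite at baseline, so that a patient with raised ALT/AST but bilirubin below its limit stays at risk for a later bilirubin rise.
3. State how many patients were already at or above each threshold, by patient group and overall, and list them, so that elevation persisting on drug stays visible.

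The cost is one derived flag, some additional outputs and SAP wording. No new data are needed. The risk set in the added curves is slightly smaller.
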